### 1. OVERVIEW AND STUDY PLAN

### 1.1. STUDY DESIGN

This is a non-inferiority, unblinded, randomized, controlled trial where 322 eligible participants undergoing IOL at  $\geq$ 37 weeks gestation at CUMC and admitted to labor and delivery unit will be enrolled and randomly assigned in a ratio 1:1 to either receive Dilapan-S® or Misoprostol for cervical ripening.

### 2. STUDY PROCEDURES

After randomization all participants will undergo assessment as per the floor protocol including Bishop score. Patients will have either 1-5 Dilapan-S® rods inserted into their cervix by the providers or receive 25 mcg of misoprostol orally every 2 hours to a maximum of 6 doses over 12 hours. Patients will be examined after 12 hours, Dilapan-S® rods will be removed and Bishop score will be reassessed. Patients in both groups will be evaluated for artificial rupture of membranes and initiation of oxytocin for inducing uterine contraction. A diagnosis of failed IOL will be made if patient does not go into active labor within 24 hours after initiation of Oxytocin and AROM. Intrapartum management will be according to institutional guidelines. All study participants will be contacted by phone 2 weeks after enrollment to find out if they needed any additional treatment following discharge. All study patients will be asked to fill out a questionnaire regarding their experience with the method of induction. Data will be collected by chart review and analysed based on the outlined statistical plan.

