Procedures - After randomization all participants will undergo assessment as per the floor protocol including Bishop Score. Patients will have either Dilapan-S[®] rods inserted into their cervix by the providers or receive 25 mcg of misoprostol orally every 2 hours to a maximum of 6 doses over 12 hours. Patients will be examined after 12 hours, Dilapan-S[®] rods will be removed and Bishop Score will be reassessed. There will be a ±30 minute window for the removal of the Dilapan-S[®] rods and ±15 minutes for Misoprostol administration. Patients in both groups will be evaluated for artificial rupture of membranes and initiation of oxytocin for inducing uterine contraction. A diagnosis of failed IOL will be made if patient does not go into active labor within 24 hours after initiation of Oxytocin and AROM. Intrapartum management will be according to institutional guidelines. All study participants will be contacted by phone 2 weeks after delivery to find out if they needed any additional treatment following discharge. All study patients will be asked to fill out a questionnaire regarding their experience with the method of induction. Data will be collected by chart review and analyzed based on the outlined statistical plan.

Title

Dilapan vs Misoprostol for cervical ripening [COMRED – comparison of Misoprostol ripening efficacy with Dilapan]

Trial Objective

To assess efficacy of Dilapan-S[®] [osmotic hygroscopic dilator] for cervical ripening compared to 25mcg of oral Misoprostol

Background

In developed countries about 25% of the pregnant women are delivered by induction of labor annually [1]. A decision to proceed with induction of labor is made when continuation of pregnancy may worsen the condition of mother or her fetus. This number is expected to go up in the future as our understanding of pathophysiology of pregnancy improves. A recent landmark randomized controlled trial involving more than 6000 nulliparous women has proved that induction of labor at 39 weeks improves perinatal outcomes without increasing the cesarean section rate compared to expectant management [2].

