- Chorioamnionitis
- Endometritis within 2 weeks after delivery,
- Postpartum hemorrhage (EBL>1000cc /and or drop in HCT by 10 points) **Neonatal outcomes:**
- Apgar score <7 at 5 min
- Cord Arterial blood pH <7
- Base excess >12mmol/l
- NICU admission within 2 weeks after delivery
- Antibiotic use within 2 weeks after delivery

Exploratory research questions (exploratory endpoints)

There is paucity of clinical data in the literature obtained through well designed clinical trials for Dilapan-S[®] use for cervical ripening in women undergoing induction of labor. We would like to collect following information for assessing safety of Dilapan-S[®] use when compared to Misoprostol. Similar information was collected by Saad et al. [12] in their recent randomized trial comparing efficacy of Dilapan-S[®] to Foley catheter for cervical ripening. These are known potential complications of planned interventions and include (but are not limited to) the following:

Undesirable side effects

- Fever, nausea, vomiting and diarrhea
- Uterine tachysystole
- Hyperstimulation
- Uterine hypertonus
- Failed induction of labor, arrest of first and second stage of labor

Complications specific to dilator insertion

- Vaginal bleeding
- Rupture of membranes
- Cervical laceration
- Excessive pain causing need for analgesia during cervical ripening
- Vasovagal reaction during insertion of the device
- Entrapment of the device
- Fragmentation of device during removal or insertion
- Retraction of device into uterine cavity.

Study subjects inclusion criteria

- 1. Women undergoing labor induction with a gestation of ≥37 weeks determined by best clinical and/or ultrasound estimation
- 2. Live fetus with in cephalic presentation
- 3. Singleton pregnancy
- 4. Able to provide informed consent for participation in the study.

Study subjects exclusion criteria

- 1. Contraindication for vaginal delivery
- 2. Age less than 18 years
- 3. Prior uterine scar from a cesarean section or myomectomy
- 4. Patients who have HELLP syndrome or eclampsia
- 5. Active genital herpes at the time of labor induction
- 6. Complex medical problems that may require assistance with second stage of labor
- 7. Bishop score ≥ 6
- 8. Major fetal congenital anomalies (as assessed by investigator)
- 9. Premature rupture of membranes

Pre-randomization training

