- Hyperstimulation (defined as > 5 contractions averaged over 20 min with abnormal fetal heart changes)[3]
- Uterine hypertonus (defined as a single contraction lasting at least 2 minutes.
- Failed induction of labor, arrest of first and second stage of labor (see Appendix 2) (defined according to the US NICHD, ACOG and SMFM workgroup guidelines [9]
- Intrapartum fever

(defined as body temperature (skin or oral) of 39°C at one reading or as body temperature of 38-38.9°C which persists when retaken after 30 minutes) [13]

Intrapartum fever when present with any of the following indicates infection may be present.

- 1. Purulent discharge on speculum exam from the cervical canal
- 2. Fetal tachycardia lasting more than 10 minutes
- 3. Maternal WBC count of more than 15 K
- 4. Amniotic fluid analysis results indicative of an infection

Postpartum and FU procedures

All participants will receive routine postpartum care. They will be asked to fill out a questionnaire (Appendix 4) in the postpartum period regarding their experience with the cervical ripening method.

All study participants will be contacted via phone two weeks after delivery to find out if they or their baby had any postpartum complication and received treatment at any health care entity other than the hospital where they were admitted for delivery.

Columbia University College of Physicians and Surgeons

Safety reporting

Scope

In relation to the **Dilapan-S**[®], the Clinical Trial is a post-market clinical follow-up study (PMCF) conducted using CE marked device within its intended use. The provisions of Directive 93/42/EEC concerning information and notification of incidents occurring following placing devices on the market are fully applicable. Medical Device Reporting regulation (21 CFR 803) will be followed to report certain device related adverse events and product problems to the FDA.

The Investigator shall ensure that Funder will be informed about any SAE that would be related to study device according to the definitions given below. Complaints about any Product Problem are within the scope of obligatory notification too, incl. product defects, malfunctions or user errors.

AEs not related to the study device are not to be reported to Funder. Borderline events should be handled conservatively and the Funder should be notified in case of any doubt.

Definitions

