# 3.2. SECONDARY OUTCOMES

Individual and composite maternal and fetal outcomes including overall vaginal delivery rate, cesarean section rate, Bishop score after cervical ripening, infections, postpartum hemorrhage. Neonatal outcomes include Apgar scores, NICU admission and sepsis.

Secondary endpoints are:

- Overall vaginal delivery rate in each group
- Rate of caesarean deliveries in each group
- Rate of operative deliveries (vaginal plus caesarean)
- Bishop score at 12 hours after the intervention and change in Bishop score
- Percentage of subjects who did not receive all 6 misoprostol doses
- Percentage of subjects with failed Dilapan-S insertion
- Percentage of subjects delivering vaginally in 24 hours after the initiation of intervention

- Delivery time
- Initiation of cervical ripening to delivery time
- Initiation of oxytocin to delivery time
- Total length of hospital stay
- Maternal outcomes:
  - Chorioamnionitis
  - Endometritis within 2 weeks after delivery
  - Postpartum haemorrhage (EBL>1000cc and/or drop in HCT by 10 points)
  - 3rd and 4th degree lacerations
- Neonatal outcomes:
  - Apgar score <7 at 5 min
  - Cord arterial blood pH and Cord arterial blood pH <7
  - Cord arterial blood base excess and Cord arterial blood base excess > -12mmol/l
  - NICU admission within 2 weeks after study intervention
  - Antibiotic use within 2 weeks after study intervention

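### The SAP times the follow-up call from enrolment and two neonatal outcomes from the study intervention, where the protocol, and the SAP's own endometritis endpoint, count from delivery

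*SAP*

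**What the plan says.** The protocol uses one time origin, delivery, for the call and for every two-week outcome:

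- Synopsis, Procedures: "All study participants will be contacted by phone 2 weeks after delivery".
- Postpartum and FU procedures: "All study participants will be contacted via phone two weeks after delivery". The stated purpose is to learn of postpartum complications in mother or baby that were treated somewhere other than the delivery hospital.
- Neonatal outcomes, under the secondary research questions: "NICU admission within 2 weeks after delivery" and "Antibiotic use within 2 weeks after delivery".

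The SAP uses three:

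- Section 2, Study Procedures (enrolment): "All study participants will be contacted by phone 2 weeks after enrollment".
- Section 3.2, neonatal outcomes (study intervention): "NICU admission within 2 weeks after study intervention" and "Antibiotic use within 2 weeks after study intervention".
- Section 3.2, maternal outcomes (delivery, as in the protocol): "Endometritis within 2 weeks after delivery".

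Neither document explains the change.

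**The concern.** The two documents give different definitions for endpoints of the same name, and a programmer working from the SAP would apply the shorter one. A baby cannot be admitted to NICU or receive antibiotics before birth, so a window that opens at rod insertion or first dose spends its first hours or days with nobody at risk. It then closes that much too early.

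Endometritis is a different case. Its definition is unchanged, but under SAP section 2 the call that would reveal treatment elsewhere takes place before the two weeks after delivery are over.

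The time removed also arises after randomisation. SAP 3.2 lists the time from start of ripening to delivery as a secondary endpoint, so the plan allows that the two methods may differ on it. A follow-up window whose length depends on that interval is not guaranteed to be equal in the two arms.

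**Working it through.** **What can be checked.** The documents give no figure for lost follow-up, so there is none to reproduce. The sample size does not enter the argument, except that 322 randomised 1:1 gives 322 / 2 = 161 per arm, used below for scale.

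**1. The anchors side by side.**

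| Item | Protocol | SAP |
|---|---|---|
| Follow-up call | delivery | enrolment |
| NICU admission | delivery | study intervention |
| Neonatal antibiotic use | delivery | study intervention |
| Endometritis | delivery | delivery |

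**2. Post-delivery time left in the SAP's neonatal windows.** Let T be the hours from intervention to delivery. The intended window is 14 × 24 = 336 hours. Time left = 336 − T; share lost = T / 336. The documents give no distribution of T, so the values below are assumptions.

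| T (hours) | Days left | Share lost |
|---|---|---|
| 24 | 312 / 24 = 13.0 | 24 / 336 = 7.1% |
| 36 | 300 / 24 = 12.5 | 36 / 336 = 10.7% |
| 48 | 288 / 24 = 12.0 | 48 / 336 = 14.3% |
| 72 | 264 / 24 = 11.0 | 72 / 336 = 21.4% |

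Intervals beyond 36 hours are plausible. The protocol's Labor Induction section allows 12 hours of ripening and then 24 hours of amniotomy with oxytocin before failed induction is diagnosed, and 12 + 24 = 36.

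Example: a baby born 36 hours after the intervention is admitted to NICU 13 days after birth. The protocol counts the admission, because 13 is less than 14. The SAP does not, because 1.5 + 13 = 14.5 days after the intervention.

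**3. The call and endometritis.** Delivery follows enrolment, so day 14 after enrolment comes before day 14 after delivery for every woman. The shortfall is T plus the gap from enrolment to intervention, which the documents do not state.

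**4. Effect on the comparison between arms.** Only a difference in T between arms biases the comparison. An assumed mean difference of 2, 6 or 12 hours is 2 / 336 = 0.6%, 6 / 336 = 1.8% or 12 / 336 = 3.6% of the window.

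To turn this into event rates, assume a constant hazard λ and a true 14-day rate r that is the same in both arms. Then λ = −ln(1 − r) / 336, and the observed rate is 1 − exp(−λ(336 − T)).

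- r = 10%: λ = 0.10536 / 336 = 0.0003136 per hour. The observed rate is 9.32% at T = 24, 9.15% at T = 30 and 8.98% at T = 36.
- Spurious difference at r = 10%: 0.17 points for 6 hours (30 v 36) and 0.34 points for 12 hours (24 v 36).
- Spurious difference at r = 5%: 0.09 and 0.17 points.

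For scale, 0.0017 × 161 is about 0.3 of one event. The standard error of a difference at a 10% rate is √(2 × 0.10 × 0.90 / 161) = 0.033, or 3.3 points. The 6-hour bias is about one-twentieth of that.

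**5. With delivery as the anchor,** every mother and baby has the full 336 hours whatever T is, so both the loss and any arm difference from this source disappear.

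**The case against.** The best defence is that little follows in practice. SAP section 2 is a narrative summary, and sites take the timing of calls from the protocol, which says delivery twice. Section 4.1 reports safety-board review in the past tense, so some data already existed when the SAP was written and its wording may not have governed those calls. The enrolment wording may well be a slip. That is a fair reading of the call. It does not reach the two neonatal definitions, which are endpoint rules in the document that governs the analysis.

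The defence can add that data also come from chart review, and that the SAP's listings include maternal readmission and neonatal post-partum data. The call therefore matters mainly for late events treated elsewhere. If neonatal events cluster soon after birth, the loss is smaller than a constant hazard suggests. Protocol and SAP 7.3 also summarise maternal and neonatal outcomes as the CRF reports them, and the CRF is not among the documents, so the windows it uses cannot be checked. All of this stands and limits the harm. None of it explains why the definitions differ.

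Two stronger readings are tempting, and the documents support neither:

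- A reader might infer that the slower arm would look safer to a degree that matters. The bias in step 4 is a fraction of a percentage point, and the documents do not show which arm is slower. The protocol's rationale says misoprostol shortens the interval to delivery, while its design assumptions put vaginal delivery within 36 hours at 65% for misoprostol and 71% for the mechanical method.
- A reader might take the complements of those two rates as the share of women still undelivered at 36 hours. They are not, because they include women delivered by caesarean before 36 hours.

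**Conclusion.** The point holds as a conflict of time origins, both between protocol and SAP and within the SAP. Applied as written, the SAP starts two neonatal windows before birth and removes 7% to 21% of the intended 14 days if delivery comes 24 to 72 hours after the intervention. Qualifying late events would then be dropped. Endometritis keeps its definition and is exposed only through a call made too early to cover its window.

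The between-arm bias is probably small: 0.09 to 0.34 percentage points across assumed differences of 6 to 12 hours and event rates of 5% to 10%, under a constant hazard. Its direction is unknown. The primary endpoint, the non-inferiority margin and the sample size are not affected. The case for correction rests on endpoints that match their protocol definitions and on complete follow-up; it does not depend on a distorted treatment comparison.

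**What to change.** - In SAP section 2, time the call two weeks after delivery instead of two weeks after enrolment.
- In SAP 3.2, count NICU admission and antibiotic use within two weeks after delivery, as the protocol does.
- Where event dates are recorded, derive these two outcomes and endometritis from delivery date and time.
- Flag women whose call took place less than 14 days after delivery, and report how many there were in each arm.

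The cost is three wording changes in the SAP, one derivation rule and one flag. The protocol does not change. Its Delivery period section already collects date and time of delivery. The documents do not show whether dates of NICU admission, antibiotic use and endometritis are recorded. If the CRF holds only yes/no answers, the SAP should state which window the CRF question used.

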### 3. OBJECTIVES

The objective of this study is to assess the efficacy of Dilapan-S® for cervical ripening compared to Misoprostol in women undergoing IOL at or more than 37 weeks gestation.

#### 3.1. PRIMARY OUTCOME

Proportion of women achieving vaginal delivery within 36 hours of intervention.

# 3.2. SECONDARY OUTCOMES

Individual and composite maternal and fetal outcomes including overall vaginal delivery rate, cesarean section rate, Bishop score after cervical ripening, infections, postpartum hemorrhage. Neonatal outcomes include Apgar scores, NICU admission and sepsis.

Secondary endpoints are:

- Overall vaginal delivery rate in each group
- Rate of caesarean deliveries in each group
- Rate of operative deliveries (vaginal plus caesarean)
- Bishop score at 12 hours after the intervention and change in Bishop score
- Percentage of subjects who did not receive all 6 misoprostol doses
- Percentage of subjects with failed Dilapan-S insertion
- Percentage of subjects delivering vaginally in 24 hours after the initiation of intervention

- Delivery time
- Initiation of cervical ripening to delivery time
- Initiation of oxytocin to delivery time
- Total length of hospital stay
- Maternal outcomes:
  - Chorioamnionitis
  - Endometritis within 2 weeks after delivery
  - Postpartum haemorrhage (EBL>1000cc and/or drop in HCT by 10 points)
  - 3rd and 4th degree lacerations
- Neonatal outcomes:
  - Apgar score <7 at 5 min
  - Cord arterial blood pH and Cord arterial blood pH <7
  - Cord arterial blood base excess and Cord arterial blood base excess > -12mmol/l
  - NICU admission within 2 weeks after study intervention
  - Antibiotic use within 2 weeks after study intervention

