
Randomization plan will be generated based on computer program. Subjects will either undergo Dilapan-S[®] insertion or receive up to 6 oral doses of 25 mcg of Misoprostol based on their allocation to treatment groups.

Baseline procedures

Subject enrolled in the study will be evaluated by a care provider and a history and physical examination including a sterile speculum and digital vaginal exam will be done. Provider will also review maternal vital signs and indication for induction of labor. All enrolled subjects will have CTG monitoring for at least 20 minutes prior to the planned intervention and IV access and Type and Screen as per the labor and delivery standard procedure.

Pre-induction

Arm A: Dilapan-S[®] group

Patients who are randomized to receive Dilapan-S[®], will have rods of Dilapan-S[®] inserted in their cervix by the supervising provider, under aseptic precautions with a speculum exam, either digitally or using a sponge forceps, as per manufacturer's recommendations [Appendix 1]. The Bishop score at the time of eligibility assessment and number of rods inserted will be recorded. Dilapan-S[®] will be left in cervix for 12 hours (±30 minutes). Patients will be allowed to ambulate, shower and have light meals as long as they meet the criteria based on institutional guidelines for intermittent fetal heart monitoring. "Nothing per vagina" including douching and no bathing is allowed.

Arm B: Misoprostol group

For subjects randomized to Misoprostol group, after the baseline assessment and a reassuring CTG monitoring for 20 minutes, 25mcg of Misoprostol will be administered orally every 2 hours (±15 minutes) to a maximum of 6 doses. All subjects will have continuous fetal monitoring. A dose will be held if patient is noted to have uterine tachysystole, hyperstimulation, fetal heart tracing abnormalities or 3 or more painful uterine contractions over a period of 10 minutes (indicating onset of labor). Administration of Misoprostol will be done by the nurse assigned to the patient.

Subjects in both groups will remain on labor and delivery (L&D) floor and will have continuous fetal monitoring as per the institutional guidelines.

All study participants will be examined after 12 hours of receiving intervention unless there is an indication for an exam prior to this period. Reasons for an exam earlier than 12 hours after the initiation of cervical ripening intervention include:

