#### 7.3. ANALYSIS OF SECONDARY ENDPOINTS

All quantitative secondary variables will be summarized separately for each arm. Means of the two treatment arms will be compared with two-sample t-test and Wilcoxon rank-sum test as appropriate.

All secondary variables involving rates and percentages, will be calculated for both arms. Difference in proportions will be derived together with a 95% two-sided confidence interval. The difference between treatment groups will be concluded if the confidence interval does not include zero.

Maternal and neonatal outcomes will be summarized as reported in the CRF.

Delivery time will be presented using Kaplan-Meier curves with censoring for caesarean delivery.

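### Two measures that each apply to one arm fall under the SAP's between-arm rule, which can declare a treatment difference with no comparative meaning

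*SAP*

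**What the plan says.** SAP section 3.2 places two process measures in its list of secondary endpoints: "Percentage of subjects who did not receive all 6 misoprostol doses" and "Percentage of subjects with failed Dilapan-S insertion". The Protocol's own list of secondary endpoints contains neither, so both were added in the SAP.

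SAP section 7.3 sets the analysis: "All secondary variables involving rates and percentages, will be calculated for both arms". It continues: "Difference in proportions will be derived together with a 95% two-sided confidence interval". The decision rule follows: "The difference between treatment groups will be concluded if the confidence interval does not include zero". A separate sentence says that maternal and neonatal outcomes will be summarised as the CRF reports them. Nothing comparable covers the two process measures. No denominator or coding is given for the arm to which a measure does not apply, and no interval method is named.

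Failure to insert Dilapan-S appears again in SAP section 3.3.2, as a safety endpoint. SAP section 7.4 reports safety variables as counts and proportions only. SAP section 6.2.1 limits the Safety population to women who had Dilapan-S placed or took misoprostol at least once, grouped by the treatment they actually had.

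The Protocol (Pre-induction, Arm B) gives the reasons for holding a dose: "A dose will be held if patient is noted to have uterine tachysystole, hyperstimulation, fetal heart tracing abnormalities or 3 or more painful uterine contractions" within 10 minutes. It describes that last criterion as a sign that labor has begun.

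**The concern.** A between-arm difference with a decision rule is informative only if the event could occur in either arm. Barring crossover, no woman assigned misoprostol can have a failed Dilapan-S insertion. Women assigned Dilapan-S either all fail to receive six misoprostol doses or have no value at all. One side of each contrast is therefore set by the design, and the hypothesis of equal rates is false or undefined before any data are seen.

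Followed literally, the plan could report one or two treatment differences with no comparative content beside real outcomes such as cesarean rate. The programmer would also have to invent a coding for the dose measure, and that choice decides which arm looks higher.

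A lesser point is that the dose measure has no clinical direction. It pools doses held because contractions had started with doses held for tachysystole, hyperstimulation or tracing abnormalities.

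**Working it through.** **Inputs.** The Protocol (Study Design) gives 153 evaluable women per arm and 322 randomised 1:1, so 322/2 = 161 per arm. Neither document gives an expected rate of failed insertion or incomplete dosing. The rates below are assumptions, shown as ranges.

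**The plan's own figure.** With rates of 65% and 71%, a margin of 10 points, one-sided 2.5% and 85% power:
n = (1.960 + 1.036)² × (0.65×0.35 + 0.71×0.29) / (0.10 + 0.06)² = 8.978 × 0.4334 / 0.0256 = 152.001, rounded up to 153. Power at 153 per arm is 85.2%, and 306/0.95 = 322.1. The stated size reproduces. It serves here only as a denominator.

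**Failed insertion, x/153 against 0/153.** The fixed arm adds no variance, so the Wald lower limit is p − 1.96 × √(p(1−p)/153), with p = x/153.
- x = 3: 1.96 − 2.20 = −0.24 points. Zero is included.
- x = 4: 2.61 − 2.53 = +0.09 points (unrounded inputs). Zero is excluded.
- x = 5: 3.27 − 2.82 = +0.45 points. Zero is excluded.

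The SAP names no interval method, and the threshold depends on it:

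| Method | Fewest failures that exclude zero | Share of 153 | Lower limit (points) |
|---|---|---|---|
| Wald | 4 | 2.6% | +0.09 |
| Score | 4 | 2.6% | +0.13 |
| Newcombe | 5 | 3.3% | +0.19 |
| Agresti-Caffo | 6 | 3.9% | +0.37 |

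The thresholds are the same at 161 per arm. Binomial chance of reaching them with 153 women:

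| Assumed true failure rate | 4 or more | 5 or more | 6 or more |
|---|---|---|---|
| 1% | 6.9% | 1.9% | 0.5% |
| 2% | 36.6% | 19.3% | 8.8% |
| 3% | 67.7% | 48.7% | 31.1% |
| 5% | 95.1% | 88.5% | 78.2% |
| 10% | about 100% | about 100% | 99.8% |

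**Incomplete dosing.** Let q be the proportion of the misoprostol arm that does not receive all six doses. Dilapan-S minus misoprostol is 100% − q if the Dilapan-S arm is coded as not having received the doses, and 0% − q if it is coded as having no event. The Wald half-width is 1.96 × √(q(1−q)/153).

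| Assumed q | Dilapan-S coded 100% | Dilapan-S coded 0% |
|---|---|---|
| 20% | +80 ± 6.3 points | −20 ± 6.3 points |
| 40% | +60 ± 7.8 points | −40 ± 7.8 points |
| 60% | +40 ± 7.8 points | −60 ± 7.8 points |

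At a more extreme q of 95% (153 of 161), with Dilapan-S coded 100%, the Newcombe interval runs from 1.6 to 9.5 points and still excludes zero. By symmetry with the failed-insertion case, zero stays inside the interval only if fewer than about 4 to 6 women complete the course (100% coding), or fewer than about 4 to 6 miss any dose (0% coding). If the Dilapan-S arm is instead treated as not applicable, no difference can be calculated.

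**Failed insertion as a safety endpoint.** Take a woman randomised to Dilapan-S in whom no rod is ever placed. Under SAP section 6.2.1 she is outside the Safety population if she takes no misoprostol, and counted under misoprostol if she does. In neither case does she appear in the Dilapan-S column, where the failure belongs.

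**The case against.** The strongest reply is that nobody intended these contrasts. Each endpoint names its own treatment. The SAP's table list keeps its analyses of proportions for vaginal delivery within 36 and 24 hours and for mode of delivery, and no table title names either process measure. Failed insertion already has a descriptive analysis under section 7.4. A reader would also see that women given misoprostol cannot have a failed Dilapan-S insertion. All of this is fair as a guess at intent. It does not amend section 7.3, which covers all secondary percentages and carves out only the maternal and neonatal outcomes. The descriptive safety route does not help either, because its population loses or misplaces the failures.

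A reader might infer that a difference is guaranteed for both measures. The documents do not support that for failed insertion. Three failures of 153 leave zero inside the Wald interval, and at a true rate of 1% the rule would be triggered at most about 7% of the time with 153 women.

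A reader might also infer that the plan treats incomplete dosing as a tolerability or safety measure. It does not. The measure sits in section 3.2 with no stated direction, and section 3.3.1 lists tachysystole, hyperstimulation and abnormal fetal heart tracing as separate safety endpoints. As a count of exposure it is legitimate. What remains is that the single percentage cannot be interpreted without reasons, and the documents do not confirm that hold reasons are captured as data. That is why the breakdown by reason is only optional.

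**Conclusion.** The point holds as a gap in secondary reporting. As written, SAP section 7.3 can declare a treatment difference on two measures that each apply to one arm only. For dosing this is near-automatic under either coding, and the two codings give opposite signs. For failed insertion it needs about 4 to 6 failures of 153, roughly 2.6% to 3.9%, depending on the interval method.

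These results assume no crossover. The 20% to 60% dosing range and the 1% to 10% insertion-failure range are illustrative and do not come from the documents. The Safety-population problem concerns women in whom no rod was ever placed.

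The primary non-inferiority test, its sample size and its power are untouched.

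**What to change.** In SAP section 7.3, state that incomplete misoprostol dosing and failed Dilapan-S insertion are exempt from the between-arm difference and from the zero-exclusion rule. Report each only within its own randomised arm, with all women randomised to that arm as the denominator and an exact (Clopper-Pearson) 95% interval. List failed insertion once, on that randomised denominator, rather than in both 3.2 and 3.3.2.

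Optionally, where the chart records it, tabulate incomplete dosing by the Protocol's hold reasons, allowing more than one per woman: contraction criterion met; tachysystole, hyperstimulation or tracing abnormality; and a residual group for anything else. The first label should not be onset of labor, because the Protocol's list of reasons for an early exam defines spontaneous labor differently, by dilation and effacement.

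The cost is a few sentences in the SAP and the loss of two comparisons that have no meaning. The optional table depends on chart data whose availability the documents do not confirm.
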